2.1 STUDY DESIGN

Observational, retrospective, multicentre study in spanish patients with metastatic Renal Cell Carcinoma (mRCC) treated with sunitinib as a first-line treatment (treatment with previous cytokine therapy is accepted) according to clinical practice who obtained a complete response (CR) to treatment in one of these 2 situations:

- a) Complete response (CR) obtained exclusively with first-line sunitinib treatment (sunitinib CR).*
- b) Response obtained after a period of time on treatment with sunitinib in which local treatment was also performed (surgery of the residual metastasis/metastases, radiofrequency ablation or radiotherapy) to achieve the total macroscopic disappearance of the disease, according to the opinion of the physician responsible for the patient (CR + local treatment).*

The patient population eligible for this study includes any patient with advanced or metastatic renal cancer treated with Sunitinib and who has achieved a CR to the tumour and its metastases at some point in the treatment and according to the usual evaluation criteria in daily clinical practice irrespective of whether it was obtained with Sunitinib alone or local treatment was required to eradicate all lesions: (residual metastasis(es), radiofrequency ablation or radiotherapy)

The requirements for a patient's inclusion are that:

- 1. These patients must have Sunitinib as first-line treatment in accordance with its Summary of Product Characteristics.*
- 2. Collection of clinical, safety and response data in patients with advanced kidney cancer.*

The study is expected to be conducted in at least 50 sites throughout Spain in order to reach the maximum number of study patients.

Case collection will start at each site after the contract with the site has been signed, all the study documentation is available and training in the procedures and objectives of the protocol has been provided by the person appointed by the sponsor.

Any number of patients that meet the inclusion criteria and no exclusion criteria may be recruited at the site.

This is an observational study designed to reflect routine clinical practice; there will be no interference with the daily routine of the medical care provided to kidney cancer patients.

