- *In cases of discontinuation of systemic treatment after a period of treatment with maintained CR, the reason for the decision and the patient's participation in this decision (whether the patient was consulted, whether it was at the patient's request or the investigator's decision).*
- *Pharmacological group by mechanism of action used in patients in the second line after disease progression: another TKI, treatment with a drug acting on the immune system.*

Exploratory analysis:

[figure not shown]
Baseline neutrophil/leukocyte ratio and evolution of the neutrophil/lymphocyte ratio throughout treatment; at 4-6 weeks, 3 months, 6 months, 9 months, 12 months and then every 6 months in the available analyses close to these dates.

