5 OBJECTIVES AND VARIABLES

The primary objective of the study is *to identify patients with metastatic renal cell carcinoma (mRCC) who obtained a complete response (CR) to treatment with Sunitinib exclusively or with Sunitinib and a local treatment to eliminate residual disease in the opinion of the clinician. Complete response (CR) is defined as the disappearance of all measurable lesions according to the investigator's criterion in at least 2 consecutive CT scans.*

The clinical baseline characteristics of these patients and the tumour will be described in order to look for predictive response factors.

[figure not shown]
The intention is to describe the therapeutic strategy used in patients who obtained the greatest clinical benefit in the cases described once the macroscopic lesions were eradicated in order to draft recommendations to be followed once the registry's statistical analysis is available.

The variables to be analysed for this study will be obtained from the patients' medical records and case report forms according to the protocol. The data will be recorded on the paper CRF designed for this study where the following patient information will be included:

DEMOGRAPHIC AND DISEASE INFORMATION

- 1) Age at the start of treatment for metastatic disease
- 2) Functional status, measured by the ECOG scale (0, 1, 2, 3, 4) and/or by means of the KPS (Karnofsky Performance Status) scale, at the start of treatment (see annex I)
- 3) Motzer and Heng prognostic criteria
- 4) Laboratory data (haemoglobin, leukocytes, corrected calcium, LDH levels, lymphocytes, platelets, neutrophils, lymphocytes)
- 5) Comorbidities
- 6) Date the disease was diagnosed
- 7) Metastasis site(s) and number
- 8) Furhrman grade (I, II, III, IV)

PFIZER CONFIDENTIAL

- 9) Tumour stage (TNM)
- 10) Previous nephrectomy
- 11) Necrosis

TREATMENT

- 1) Start date of treatment with first-line Sunitinib
- 2) Initial dose and treatment regimen
- 3) Type of treatment received (monotherapy or in combination with local treatment) and technique used in the case of local treatment
- 4) Response to treatment.
- 5) Date of completion of the treatment after CR if treatment is interrupted
- 6) Modification of dosage and/or treatment regimen, number of changes in the dose, reason, date and new dose
- 7) Dose interruptions, number of interruptions, reason, date of interruption and restart and new dose

CCI

- 9) Adverse reactions

POST-TREATMENT

- 1) Continuation of treatment in 1st line

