- 2) End date and reason
- 3) Date of progression
- 4) Date of and reason for death
- 5) Post-Sunitinib treatments (another TKI, mTOR, immunotherapy)

The following aspects will be assessed using the variables collected:

- **Time from nephrectomy to the start of systemic treatment:** defined as the time interval from the day of the nephrectomy to the day treatment with Sunitinib started.
- **Time to CR:** defined as the time interval from the day treatment with Sunitinib started until the day the complete response is documented in the first CT scan without lesions.
- **Duration of treatment with Sunitinib once CR is reached:** defined as the time interval from the day on which the complete response is documented until the day that the definitive discontinuation of the treatment is confirmed, either at the patient's own decision or at the doctor's decision.
- **Time to progression (TTP):** defined as the time interval from the day on which the complete response is documented until the first day that objective tumour progression, if any, is observed.
- **Time to change of treatment:** in patients who continue treatment with Sunitinib once the lesions have disappeared, it is defined as the time interval from the day on which the complete response is documented until the first day on which the change of treatment due to unacceptable toxicity is documented, as applicable.
- **Time to death:** defined as the time interval from the day on which the

Pfizer Confidential

complete response is documented to the day on which death from any cause is documented, if it occurs.

- **Duration of complete response (DOR):** defined as the time interval from the date on which the complete response to Sunitinib is identified until the date of the CT scan conforming tumour progression, the change of treatment due to unacceptable toxicity, death from any cause or until the date of the last follow-up at the close of the study. It represents the time that the patient survives without signs of disease.

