7.2 STATISTICAL ANALYSIS

7.2.1. Included and evaluable population

The descriptive statistics of patients who meet all the inclusion criteria and none of the exclusion criteria will be presented.

In the subpopulation of non-evaluable patients, their frequency distribution will be presented, depending on the reasons for non-eligibility:

[figure not shown]
- Patients who are not 18 years of age or older and who have been treated for metastatic renal carcinoma with Sunitinib as first-line (prior cytokine treatment is admitted) between 2007 and October 30, 2018.
- Patients aged 18 years or older who have been treated for a metastatic renal carcinoma with Sunitinib as second line.
- Patients aged 18 years or older who have been treated for a metastatic renal carcinoma with Sunitinib as first line (prior cytokine treatment is admitted) between 2007 and October 30, 2018 and who have not obtained, as best response to treatment, total disease remission in the opinion of the treating physician from the clinical, radiological and/or macroscopic standpoint.
- Patients whose duration of CR has not been confirmed with at least 2 consecutive imaging tests, with no limit on the duration of this response.
- Patients treated with another drug other than Sunitinib.
- Patients without radiology reports that substantiate the CR.
- Patients without a record of the dose and regimen of Sunitinib.
- Patients who achieved complete remission after October 30, 2018.

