 - Active participation by the patient in the decision to discontinue the product once CR is reached
 - At the patient's decision
 - At the doctor's decision
 - Other reasons
 - Calculation of total days of treatment interruption

A summary calculation of the dose modifications will be made for the aspects described above. For the calculation of total days of interruption of treatment, descriptive central tendency (mean, median) and dispersion (standard deviation, interquartile range)

PFIZER CONFIDENTIAL

statistics will be presented.

- **Post-treatment.** The absolute and relative frequency of the number of patients who discontinue first-line Sunitinib treatment will be reported definitively after the CR. In the subpopulation of patients who remain on second-line treatment, frequency distribution will be presented for:
 - o Reason for terminating the treatment:
 - Toxicity
 - Progression
 - Death, reason:
 - Progression
 - Toxicity, in this case:
 - ✓ In the investigator's opinion related to Sunitinib
 - ✓ Not related to Sunitinib
 - Another reason
 - o Total number of days of duration of treatment with second-line Sunitinib.
 - o Post-second-line Sunitinib pharmacological treatment group after disease progression after a period of CR:
 - TKI
 - mTOR
 - Immunotherapy

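### SAP 7.2.3 limits the stopping-reason, duration and next-drug items to patients on second-line treatment, so no specified table gives all reasons over everyone who definitively ended first-line sunitinib after CR

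*SAP*

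**What the plan says.** The Post-treatment item of SAP 7.2.3 opens with a count: "The absolute and relative frequency of the number of patients who discontinue first-line Sunitinib treatment will be reported definitively after the CR". The adverb is misplaced, but the group is clear: patients whose first-line sunitinib ended for good after CR.

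The next sentence moves to another group: "In the subpopulation of patients who remain on second-line treatment, frequency distribution will be presented for". Three items follow:

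- why treatment ended (toxicity, progression, death with its cause, another reason);
- "Total number of days of duration of treatment with second-line Sunitinib";
- the class of drug given next (TKI, mTOR, immunotherapy), also described as coming after second-line sunitinib.

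Elsewhere the line of treatment is not in doubt. SAP 2.1 requires: "These patients must have Sunitinib as first-line treatment in accordance with its Summary of Product Characteristics". A secondary objective in SAP 2.2 places second line after the disease has progressed: "Pharmacological group by mechanism of action used in patients in the second line after disease progression". The post-treatment variables in SAP 5 include "Continuation of treatment in 1st line" and "End date and reason", neither of them limited to patients who reached second line.

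SAP 7.2.4 separately promises the most frequent reasons for stopping, and who took the decision, in patients who discontinue while CR is maintained.

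**The concern.** The two preceding blocks of SAP 7.2.3, on dose modifications and temporary interruptions, each count a group and then break down that same group. The Post-treatment block counts one group and breaks down another. That looks like a drafting slip, but a programmer who follows the text would build the table on the wrong patients.

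The registry was set up to review what was done after CR, so that recommendations can be drafted. For that purpose a reader needs the shares of stopping by choice in CR, for toxicity, for progression and by death, all over one denominator. Membership of the table as specified depends on something that happens later, namely reaching a further line of therapy. If the shell is left as it is, the choice of denominator will be made after the data have been seen.

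**Working it through.** The plan gives no figure to reproduce, so the check is a comparison of texts.

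**Step 1: can the treatment that ended be first-line sunitinib?** Then everyone in the table started another line afterwards. Death is a listed reason, yet nobody whose first line ended in death could be in the group. That category would be empty by construction.

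**Step 2: can it be second-line treatment?** Then the table gives reasons for ending a treatment that its members, by definition, *remain* on. Duration would be duration of sunitinib in second line. SAP 5 defines no re-treatment variable in its legible text (one item in its Treatment list is blacked out). The next-drug item, read literally, would describe a line later than the one named in the SAP 2.2 objective.

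Neither reading is coherent.

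**Step 3: who is covered?** The possible courses after CR are set against the two places where reasons for definitive stopping are reported. A stop for toxicity while in CR is placed in the maintained-CR rows.

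| Course after CR | SAP 7.2.3 reason table | SAP 7.2.4 maintained-CR reasons |
|---|---|---|
| Still on first-line sunitinib | no, rightly | no, rightly |
| Stopped with CR maintained, no relapse | no | yes |
| Stopped with CR maintained, relapsed, started second line | yes | yes |
| Stopped with CR maintained, relapsed, no second line | no | yes |
| Stopped for progression, started second line | yes | no |
| Stopped for progression, no second line | no | no |
| Died on first-line sunitinib | no | no |

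Six of the seven courses involve an ended first line. SAP 7.2.3 covers two and SAP 7.2.4 covers three, with one in common: 2 + 3 − 1 = 4. That leaves 6 − 4 = 2 courses in neither. These are kinds of course, not patient counts. If *remain* is taken strictly, patients who started second line and had already ended it also leave the 7.2.3 table.

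**Step 4: are the data there?** Yes. SAP 5 lists first-line continuation, end date and reason, progression date, date and cause of death, and later treatments. The Variables table in the protocol adds definitive interruption after CR and the patient's part in that decision.

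**The case against.** The strongest reply is that the three items describe re-treatment with sunitinib after relapse. The SAP introduction reports this in the Czech registry, where 4 of the 12 patients given second-line therapy received the same drug again. On that reading death is a possible reason and the denominator is deliberate. What stands is that the wording is ambiguous, and that treating the terminated drug as first-line sunitinib is an inference. What does not stand is that re-treatment rescues the text: it still clashes with *remain*, and no re-treatment variable is defined in the legible text.

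A second reply is that most of the information appears elsewhere. This is largely right. SAP 7.2.4 reports reasons and decision-maker for stopping in maintained CR. The interruption block of 7.2.3 has CR as a reason, split by patient's or doctor's decision. Time on sunitinib after CR is summarised in 7.2.2, and progression, toxicity-related change and death enter the Kaplan-Meier analyses. A reader might infer that reasons for stopping in sustained CR go unreported; they do not. But 7.2.4 promises only the most frequent reasons in one sub-sample, the interruption block concerns temporary stops, and the survival analyses give times rather than a distribution of reasons.

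A reader might also take the second-line patients of 7.2.3 to be those whom SAP 7.2.1 makes non-evaluable: "Patients aged 18 years or older who have been treated for a metastatic renal carcinoma with Sunitinib as second line". The documents do not support that. The item in 7.2.1 concerns eligibility, and a patient who reached CR on first-line sunitinib and was later re-treated meets the criterion.

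**Conclusion.** The table is wrong as written. Its denominator and line label do not fit its own reason categories, the first-line design or the variables collected. It selects towards patients who relapsed, and it omits those who stopped without relapse and those who progressed or died without second-line treatment. The consequence is limited: no specified table shows all reasons over all definitive discontinuers.

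No numerical size can be given. A reader might apply the Czech registry figures, 12 of 30 discontinuers reaching second line (40%), and conclude that the table would cover that share and show almost only progression. Neither follows. Those 30 stopped after reaching CR, and 14 of them progressed later, so the 12 would carry reasons other than progression. All 30 also appear to be the kind of patient whom SAP 7.2.4 describes. For the whole cohort the SAP gives 65 stopping without relapse, 18 for progression and 17 still treated (65 + 18 + 17 = 100), with no second-line count for the 65 + 18 = 83 who had stopped.

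The conclusion assumes that second line normally follows progression, as SAP 2.2 has it. A change of drug for toxicity during CR, if counted as second line, would be an exception. The study is descriptive, and no test, sample size or primary result is affected. The point should be corrected before tables are programmed.

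**What to change.** In the Post-treatment item of SAP 7.2.3:

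1. Define the denominator for reason and duration as all patients who definitively ended first-line sunitinib after CR, by any route including death. Show the number still on first-line sunitinib beside it.
2. Relabel the duration as that of first-line sunitinib.
3. Add stopping in maintained CR as a reason category, split by patient's or doctor's decision. State that the SAP 7.2.4 sub-sample is a subset of this denominator, so that the counts reconcile.
4. Report second-line drug class (TKI, mTOR, immunotherapy) in a separate table, restricted to patients who started second line after progression.
5. If sunitinib re-treatment is of interest, define it as its own variable and confirm that the CRF records it.

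Items 1 to 4 need SAP wording and one table shell split in two. They use data already planned for collection and change no sample size or test. Item 5 arises only if re-treatment was what the text meant.

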7.2.4. Efficacy analysis

Depending on the **primary objective of the study**, the complete responses (CR) observed in Spanish daily clinical practice in patients with advanced carcinoma with a renal cell component that have received first-line treatment with Sunitinib will be described. All demographic and clinical characteristics will be summarised descriptively.

More specifically, the following baseline features of both patient and tumour will be described:

- Demographic characteristics (age at the start of treatment of the metastatic disease).
- Comorbidities: presence of cardiovascular, hepatic, renal, autoimmune, chronic dermatological, obesity and/or intestinal disease.
- Tumour data: number and site of metastases, tumour histology, Fuhrman grade and presence of tumour necrosis.
- Previous nephrectomy in the treatment of metastatic renal cancer and time elapsed from nephrectomy to the start of systemic treatment.
- Classification of the risk group according to Motzer and/or Heng criteria.
- Patient's baseline status, including ECOG grade, presence of anaemia, corrected calcium, LDH levels, neutrophil and platelet levels.

Central tendency measures (mean and median) and dispersion measures (standard deviation and interquartile range) will be used for the quantitative variables. Frequency distributions (absolute and relative) will be presented for categorical data. Bivariate comparisons between baseline characteristics and events of interest of a continuous nature will be made by parametric tests (Student's t test, one-way ANOVA) or their non-parametric equivalents (Mann-Whitney, Kruskal-Wallis) depending on the distribution of the variables. In the case of categorical variables, the Chi-squared test or Fisher's exact

PFIZER CONFIDENTIAL

test, as applicable, will be used for the comparison of frequency distribution.

The **secondary outcome measures** pertaining to the follow-up time until the event of interest (complete disease remission, disease progression, change of treatment due to unacceptable toxicity or death from any cause) will be described by estimating survival functions using the Kaplan-Meier method. Specific estimates and 95% confidence intervals will be provided for the median, 25th percentile and 75th percentile of the distributions of each secondary variable. The secondary outcome variables related to follow-up time are:

- Time on treatment with Sunitinib until complete remission of lesions, calculated as the difference between treatment start date and CR confirmation date (2nd CT scan).
- Duration of complete remission (DOR)
- Progression-free survival (PFS) or time from remission to disease progression, change of treatment due to unacceptable toxicity or death. It will be calculated as the time elapsed from the RC confirmation date (2nd CT scan) until the date of progression/death or change of treatment for unacceptable toxicity, as applicable, or else it will be censored on the date of the last patient follow-up.

Taking into account the asymmetry normally observed in the distribution of survival times and that follow-up periods may be uneven (different study entry date), the Kaplan-Meier method will be used to estimate the median time to CR together with its 95% confidence interval. The median will indicate when complete remission of the disease occurred in 50% of patients.

In order to find associations between time to CR and the baseline features of both patient and tumour, a log-rank test will be used for comparison between groups and the determination of the statistical significance of the correlation between each of the baseline variables and the time to complete remission of disease. The following baseline characteristics are considered:

[figure not shown]
- Demographic characteristics
- Comorbidities
- Tumour data
- Prior nephrectomy in the treatment of metastatic renal cancer
- Classification of the risk group according to Motzer and/or Heng criteria.
- Patient's baseline status, including ECOG grade, presence of anaemia, corrected calcium, LDH levels, neutrophil and platelet levels.

This analysis will establish which baseline characteristics are associated with a shorter complete response time to treatment.

As part of the secondary objectives, the doses and treatment regimens observed in the sample will also be descriptively summarised by means of absolute and relative frequencies. In the case of changes in the treatment dose, the frequency of patients with dose increase, dose reduction and changes in the rest regimen will be specified. Similarly, the most frequent reasons for changes in dosage and/or treatment regimen to RC will be reported.

Frequencies of the type of treatment received will be presented, depending on whether it

Pfizer Confidential

is monotherapy or combination with a local treatment for one or several residual lesions. In the group of patients who received local treatment, the frequency distribution of the techniques used (traditional surgery, radiotherapy and SBRT) will be presented, at the time they are applied, as well as histology, degree of tumour necrosis and the surgical complications reported.

In the sub-sample of patients who discontinue systemic treatment after a period of treatment with maintenance of CR, the most frequent reasons for the decision and the frequency of cases in which the patient was consulted in the decision to discontinue treatment will be reported, and the cases in which it was at the patient's or the investigator's request.

The distribution of frequencies of the pharmacological group by mechanism of action used in patients in the second-line treatment after disease progression will be reported.

Once the descriptive statistics have been presented, and provided that the proportional *hazards* assumption or relative risk of the covariates of interest (patient and tumour baseline conditions, dose and treatment regimen and type of treatment received) are fulfilled, a multivariate Cox regression will be performed to investigate the effect of all prognostic factors on CR/PFS. The *hazards ratio* (HR) will be estimated, along with their 95% confidence intervals, as parameters of association between each one of the predictive factors of response and the time to complete remission or disease progression.

This information will make it possible to produce recommendations for the therapeutic strategy to be followed in patients who obtain complete remission of the macroscopic lesions to the treatment with Sunitinib.

For the safety analysis of treatment with Sunitinib, the percentage of patients who have presented serious and non-serious adverse events explicitly attributed to Sunitinib during treatment will be presented by means of descriptive tables. The frequency of adverse events recorded will be reported based on severity, the highest grade and whether it or they led to a dose interruption or modification.

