7.2.2. Descriptive analysis

The mean value, standard deviation, median, minimum, maximum, interquartile range (RIQ) and 95% confidence interval (CI 95%) of the following variables will be provided:

- Age of the patients at the start of treatment.
- Pre-treatment necrosis percentage

PFIZER CONFIDENTIAL

[figure not shown]

- Laboratory data at the start of treatment:
 - Haemoglobin
 - Leukocytes
 - Corrected calcium
 - LDH levels
 - Lymphocytes
 - Platelets
 - Neutrophil/Lymphocyte rate
- Time elapsed from the nephrectomy to the start of systemic treatment
- Time on treatment until CR is reached
- Duration of CR
- Time on treatment after CR is reached

The frequency distribution of patients will be presented according to:

[figure not shown]
- ECOG:
 - 0
 - 1
 - 2
 - 3
 - 4
- KPS (Karnofsky Performance Status):
 - 0%
 - 10%
 - 20%
 - 30%
 - 40%
 - 50%
 - 60%
 - 70%
 - 80%
 - 90%
 - 100%
- Motzer prognostic criteria:
 - Favourable (0 factors)
 - Intermediate (1-2 factors)
 - Poor (3 or more factors)
- Heng prognostic criteria:
 - Favourable (0 factors)
 - Intermediate (1-2 factors)
 - Poor (3 or more factors)
- Comorbidities:

PFIZER CONFIDENTIAL

- Cerebrovascular disease
 - Liver disorders
 - Renal failure
 - Autoimmune disease
 - Chronic dermatological disease
 - Obesity
 - Bowel disease
- Metastasis site:
 - Lung
 - Liver
 - Brain
 - Pancreas
 - Nodes
 - Other
- Fuhrman grade:
 - I
 - II
 - III
 - IV
- TNM tumour stage
- Histological type:
 - Clear cell
 - Chromophobe
 - Sarcomatoid, percentage
 - <20%
 - 20-30%
 - 31-50%
 - 51-75%
 - >75%
 - Papillary type 1
 - Papillary type 2
 - Mixed
 - Not performed
- Previous nephrectomy:
 - Yes
 - No
- Complications during surgery:
 - Yes
 - No
- Initial dose and treatment regimen:

PFIZER CONFIDENTIAL

- Sunitinib 50 mg 4/2 regimen
- Sunitinib 50 mg 2/1 regimen
- Sunitinib 37.5 mg 4/2 regimen
- Sunitinib 37.5 mg 2/1 regimen
- Sunitinib 25 mg 4/2 regimen
- Sunitinib 25 mg 2/1 regimen

- Type of treatment received:

- Sunitinib monotherapy
- Sunitinib + subsequent local treatment
- Local treatment techniques for residual lesions:
 - Traditional surgery
 - Radiotherapy
 - SBRT

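### SAP 7.2.2 summarises duration of CR and time on sunitinib after CR as if fully observed, and 7.2.4 names no censoring-aware group test for times measured from CR

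*SAP*

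**What the plan says.** SAP 7.2.2 lists the continuous variables for which it wants "The mean value, standard deviation, median, minimum, maximum, interquartile range" and a 95% confidence interval. Alongside age and laboratory values, the list includes duration of CR and time on treatment after CR. The section does not mention censoring.

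SAP 5 defines DOR as ending at progression, change of treatment for toxicity, "death from any cause or until the date of the last follow-up at the close of the study". Time on sunitinib after CR ends at definitive discontinuation, with no rule for a patient still on treatment when the data are collected.

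SAP 7.2.4 first deals with the primary objective: "Bivariate comparisons between baseline characteristics and events of interest of a continuous nature will be made by parametric tests" (Student's t, one-way ANOVA) or by Mann-Whitney or Kruskal-Wallis, depending on distribution. It does not say which variables these are. The next paragraph turns to the secondary outcomes and uses the term event of interest for "complete disease remission, disease progression, change of treatment due to unacceptable toxicity or death from any cause) will be described by estimating survival functions" by Kaplan-Meier. The times listed there are time to CR, DOR and progression-free survival (PFS) from CR. PFS without an event has an explicit rule: "or else it will be censored on the date of the last patient follow-up". The SAP also notes that "follow-up periods may be uneven (different study entry date), the Kaplan-Meier method will be used to estimate the median time to CR". Log-rank comparison of baseline groups is specified for time to CR only. A multivariate Cox model on CR/PFS follows, provided that proportional hazards holds.

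**The concern.** A patient still in CR at last follow-up contributes a lower limit for DOR, not a DOR. The same holds for a patient still on sunitinib. A mean, SD, ordinary median or t-based interval that takes these values as complete runs low, by an amount that depends on follow-up. Median duration of CR is a secondary objective, and the final report would carry two different medians for it: one from 7.2.2 and one from the Kaplan-Meier analysis in 7.2.4.

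The second issue is a gap in the group comparisons. The only bivariate test in the SAP that handles censoring is assigned to time to CR. Every included patient has reached CR (SAP 4.1.1), so that is the one time with no censoring. For DOR, PFS from CR and time on sunitinib after CR, no bivariate test is clearly assigned, while an undefined phrase leaves t and rank tests available. CRs dated from 2007 to October 2018 have very different follow-up. If a baseline feature goes with calendar period, such a test could report unequal follow-up as a predictor of durable CR. SAP 7.2.4 says that its results will support treatment recommendations.

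**Working it through.** The plan gives no error rate, event count or power figure on this point, so there is none to reproduce.

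**Inputs.** About 90 patients (SAP 4.1). Significance at 0.05 (SAP 3.2; two-sided assumed). Data collection to 31 July 2019 (Protocol 8.5). CR no later than 30 October 2018 (SAP 4.1.2). Background medians from CR of 7.9 and 27.6 months (SAP 2).

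**Assumptions.** Exponential DOR. CR dates from about January 2008, so follow-up from CR runs from 9 to 138 months, uniformly distributed.

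**Summaries in 7.2.2.** Let λ = ln 2 / median, so the true mean is 1/λ. With follow-up uniform on 9-138 months, the expected proportion censored is q = (e^(−9λ) − e^(−138λ)) / (129λ). The expected observed time is (1 − q)/λ.

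- Median 27.6: λ = 0.02511 and 1/λ = 39.8. q = (0.7977 − 0.0313)/3.240 = 0.237. Observed mean = 39.8 × 0.763 = 30.4 months, 24% low.
- Median 7.9: λ = 0.08774 and 1/λ = 11.4. q = (0.4540 − 0.0000)/11.318 = 0.040. Observed mean = 11.4 × 0.960 = 10.9 months, 4% low.

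The ordinary median solves 2^(−t/27.6) × (138 − t)/129 = 0.5. At t = 23.0 this is 0.561 × 0.891 = 0.500, so the median is reported as about 23 instead of 27.6. With a true median of 7.9 nobody is censored before the median (minimum follow-up is 9 months), so the ordinary median is not biased.

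By simulation with n=90, the 95% CI of the mean covers the true mean in about 11% of datasets at median 27.6 and about 90% at median 7.9. None of this needs any difference between groups.

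**Group tests, if applied to a censored time.** Two groups of 45, identical DOR, 4,000 runs per scenario, two-sided 0.05. The t and Mann-Whitney tests use the observed time; the log-rank uses time and censoring status. False-positive rates at median 27.6 months:

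| Follow-up, months | t | Mann-Whitney | Log-rank |
|---|---|---|---|
| 9-138 in both groups | 4.9% | 5.3% | 5.1% |
| 9-138 vs 9-100 | 9.1% | 6.2% | 5.1% |
| 40-138 vs 9-100 | 24.4% | 15.9% | 5.5% |
| 74-138 vs 9-74 (no overlap) | 64.7% | 34.0% | 5.1% |

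In the last row the observed means are 36.7 and 24.2 months, although true DOR is the same. At median 7.9 months the t test is at most 6.4% and Mann-Whitney at most 5.3% in all four scenarios, because about 96% of patients have the event. At an assumed median of 60 months, which is not in the documents, the t test ranges from 21% to 99% over the three unequal scenarios.

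**Time to CR.** With no censoring (median 10.1 months, SAP 2), t, Mann-Whitney and log-rank give 5.2%, 4.6% and 5.7%. There is no bias here.

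**The case against.** The sentence on t and rank tests stands in the primary-objective paragraph, directly after the baseline summaries, and is followed by the chi-squared rule for categorical variables. It can be read as generic text on choosing a test by variable type. The paragraph on secondary outcomes then sends the event times to Kaplan-Meier, with censoring stated for PFS and uneven follow-up acknowledged. Cox on PFS already gives a censoring-aware association analysis for nearly the same quantity as DOR: the two end on the same events and differ mainly in whether they start at the first or the second CT scan. The association objective concerns CR, and the stated objective for DOR is only its median. This is also an exploratory registry without hypotheses.

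Most of this stands. A reader might infer that the SAP orders t tests on censored durations; it never says so. A reader might also take an extreme case as the expected size. Follow-up of 6-48 against 48-130 months gives 96% for the t test at median 27.6, but those windows do not overlap and no document supports them. Because the SAP chooses the test by distribution and expects skewed times, Mann-Whitney is the likelier choice, and its inflation is smaller. Nor would every feature linked to calendar time look predictive: with short DOR there is almost no inflation.

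The objection does not remove three things. Section 7.2.2 names the two censored durations outright. No bivariate log-rank is named for DOR or PFS, and the Cox model depends on proportional hazards. Time on sunitinib after CR is not in the Kaplan-Meier list, so it has no censoring-aware method anywhere in the SAP.

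**Conclusion.** The point holds for 7.2.2 as written. Duration of CR and time on sunitinib after CR are listed for complete-data summaries, and the DOR entry conflicts with 7.2.4. Under the stated assumptions the mean of DOR is between 4% low (true median 7.9 months) and 24% low (27.6 months), with CI coverage of about 90% and 11%. The ordinary median is unbiased in the first case and about 23 instead of 27.6 in the second. The size depends on the assumed exponential shape and follow-up range.

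For 7.2.4 the finding is an ambiguity, not a stated error. If t or rank tests were used on DOR, PFS from CR or time on sunitinib after CR, the false-positive rate would be about 5% with equal follow-up and close to that with short DOR. At median 27.6 months it would rise to about 25% (t) and 16% (Mann-Whitney) with partly overlapping follow-up, and to 65% and 34% with none. The documents give no figure for how follow-up differs between baseline groups, so no single value can be put forward as the expected one. Time to CR is not affected.

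**What to change.** - **SAP 7.2.2:** for duration of CR and time on sunitinib after CR, replace the mean, SD, ordinary median and their CI with Kaplan-Meier median and quartiles with 95% CIs, censored at last follow-up.
- **SAP 7.2.4:** limit t, ANOVA, Mann-Whitney and Kruskal-Wallis to uncensored variables, and list them.
- **SAP 7.2.4:** name log-rank, together with the Cox model already planned, for DOR, PFS from CR and time on sunitinib after CR. Add the last of these to the Kaplan-Meier list.

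In the simulation, log-rank on these times gives 4.9-6.1% false positives across all 16 scenarios of median and follow-up. The cost is SAP wording only: the methods are already in the plan, and the dates needed are already on its list of data to collect.
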